15.4 Analysis of Secondary Endpoints

As a secondary analysis we will explore if NAC treatment decreases levels of NO in exhaled breath or the numbers of eosinophils in peripheral blood.

15.5 Interim Analysis

No interim analysis is planned.

15.6 Sample Size and Randomization

We propose a sample size of 30, which will provide us with the power to examine the effect of NAC in a subgroup of individuals with asthma who have CT evidence of intraluminal mucus and to identify the CT mucus score that performs best as a biomarker of treatment response to NAC. Participants will be enrolled if their CT mucus scores are ≥ 5.0 . To calculate sample size for the one-week treatment period study, we used FEV1 measures from 219 adults with asthma published in Corren et al. NEJM, 2011¹. The authors found that the standard deviation for the change in FEV1 in liters from day 1 to day 7 was 19%. Using a standard deviation of 19 and a two-sided alpha of 0.05, we calculate a sample size of 30 to have 80% power to detect a change in FEV1 of 10% (a reasonable effect size because early studies of Pulmozyme in CF reported a 10% increase in FEV1 at day 3 of treatment).⁷

16 DATA COLLECTION, RETENTION AND MONITORING

16.1 Data Collection Instruments

The Investigator will prepare and maintain adequate and accurate source documents designed to record all observations and other pertinent data for each subject treated with the study drug.

Study personnel at each site will enter data from source documents corresponding to a subject's visit into the protocol-specific paper CRF when the information corresponding to that visit is available. Subjects will not be identified by name in the study database or on any study documents to be collected by the Sponsor (or designee), but will be identified by a site number, subject number and initials. If a correction is made on a CRF, the study staff member will line through the incorrect data, write in the correct data and initial and date the change.

The Investigator is responsible for all information collected on subjects enrolled in this study. All data collected during the course of this study must be reviewed and verified for completeness and accuracy by the Investigator. A copy of the CRF will remain at the Investigator's site at the completion of the study.

16.2 Data Management Procedures

The data will be entered into a validated database. The Data Management group will be responsible for data processing, in accordance with procedural documentation. Database lock will occur once quality assurance procedures have been completed.

All procedures for the handling and analysis of data will be conducted using good computing practices meeting FDA guidelines for the handling and analysis of data for clinical trials.

16.3 Data Quality Control and Reporting

After data have been entered into the study database, a system of computerized data validation checks will be implemented and applied to the database on a regular basis. Query reports (Data Clarification Requests) pertaining to data omissions and discrepancies will be forwarded to the clinical research coordinators for resolution. The

study database will be updated in accordance with the resolved queries. All changes to the study database will be documented.

16.4 Archival of Data

The database is safeguarded against unauthorized access by established security procedures; appropriate backup copies of the database and related software files will be maintained. Databases are backed up by the database administrator in conjunction with any updates or changes to the database.

At critical junctures of the protocol (e.g., production of interim reports and final reports), data for analysis is locked and cleaned per established procedures.

16.5 Availability and Retention of Investigational Records

The Investigator must make study data accessible to the monitor, other authorized representatives of the Sponsor (or designee), IRB/IEC, and Regulatory Agency (e.g., FDA) inspectors upon request. A file for each subject must be maintained that includes the signed Informed Consent, HIPAA Authorization and copies of all source documentation related to that subject. The Investigator must ensure the reliability and availability of source documents from which the information on the CRF was derived.

All study documents (patient files, signed informed consent forms, copies of CRFs, Study File Notebook, etc.) must be kept secured for a period of two years following marketing of the investigational product. There may be other circumstances for which the Sponsor is required to maintain study records and, therefore, the Sponsor should be contacted prior to removing study records for any reason.

16.6 Monitoring

Monitoring visits will be conducted by representatives of the Sponsor according to the U.S. CFR Title 21 Parts 50, 56, and 312 and ICH Guidelines for GCP (E6). By signing this protocol, the Investigator grants permission to the Sponsor (or designee), and appropriate regulatory authorities to conduct on-site monitoring and/or auditing of all appropriate study documentation.

16.7 Subject Confidentiality

In order to maintain subject confidentiality, only a site number, subject number and subject initials will identify all study subjects on CRFs and other documentation submitted to the Sponsor. Additional subject confidentiality issues (if applicable) are covered in the Clinical Study Agreement.

17 ADMINISTRATIVE, ETHICAL, REGULATORY CONSIDERATIONS

The study will be conducted according to the Declaration of Helsinki, Protection of Human Volunteers (21 CFR 50), Institutional Review Boards (21 CFR 56), and Obligations of Clinical Investigators (21 CFR 312).

To maintain confidentiality, all laboratory specimens, evaluation forms, reports and other records will be identified by a coded number and initials only. All participant interviews/visits are conducted in private testing rooms. Information about study

participants is kept in study binders in a locked storage closet, and in our password protected secure electronic file, and is only accessible to authorized study personnel. Clinical information will not be released without written permission of the subject, except as necessary for monitoring by the FDA. The Investigator must also comply with all applicable privacy regulations (e.g., Health Insurance Portability and Accountability Act of 1996, EU Data Protection Directive 95/46/EC).

17.1 Protocol Amendments

Any amendment to the protocol will be written by the Sponsor. Protocol amendments cannot be implemented without prior written IRB/IEC approval except as necessary to eliminate immediate safety hazards to patients. A protocol amendment intended to eliminate an apparent immediate hazard to patients may be implemented immediately, provided the IRBs are notified within five working days.

17.2 Institutional Review Boards and Independent Ethics Committees

The protocol and consent form will be reviewed and approved by the IRB/IEC of each participating center prior to study initiation. Serious adverse experiences regardless of causality will be reported to the IRB/IEC in accordance with the standard operating procedures and policies of the IRB/IEC, and the Investigator will keep the IRB/IEC informed as to the progress of the study. The Investigator will obtain assurance of IRB/IEC compliance with regulations.

Any documents that the IRB/IEC may need to fulfill its responsibilities (such as protocol, protocol amendments, Investigator's Brochure, consent forms, information concerning patient recruitment, payment or compensation procedures, or other pertinent information) will be submitted to the IRB/IEC. The IRB/IECs written unconditional approval of the study protocol and the informed consent form will be in the possession of the Investigator before the study is initiated. The IRB/IECs unconditional approval statement will be transmitted by the Investigator to the Sponsor or designee prior to the shipment of study supplies to the site. This approval must refer to the study by exact protocol title and number and should identify the documents reviewed and the date of review.

Protocol and/or informed consent modifications or changes may not be initiated without prior written IRB/IEC approval except when necessary to eliminate immediate hazards to the patients or when the change(s) involves only logistical or administrative aspects of the study. Such modifications will be submitted to the IRB/IEC and written verification that the modification was submitted and subsequently approved should be obtained.

The IRB/IEC must be informed of revisions to other documents originally submitted for review; serious and/or unexpected adverse experiences occurring during the study in accordance with the standard operating procedures and policies of the IRB; new information that may affect adversely the safety of the patients of the conduct of the study; an annual update and/or request for re-approval; and when the study has been completed.

17.3 Informed Consent Form

Informed consent will be obtained in accordance with the Declaration of Helsinki, ICH GCP, US Code of Federal Regulations for Protection of Human Subjects (21 CFR

50.25[a,b], CFR 50.27, and CFR Part 56, Subpart A), the Health Insurance Portability and Accountability Act (HIPAA, if applicable), and local regulations.

The Investigator will prepare the informed consent form and HIPAA authorization for submission to the IRB/IEC. The consent form generated by the Investigator must be acceptable and be approved by the IRB/IEC. The written consent document will embody the elements of informed consent as described in the International Conference on Harmonisation and will also comply with local regulations.

A properly executed, written, informed consent will be obtained from each subject prior to entering the subject into the trial. Information should be given in both oral and written form and subjects must be given ample opportunity to inquire about details of the study. A copy of the signed consent form will be given to the subject and the original will be maintained with the subject's records.

17.4 Publications

The preparation and submittal for publication of manuscripts containing the study results shall be in accordance with a process determined by mutual written agreement among the study Sponsor and participating institutions. The publication or presentation of any study results shall comply with all applicable privacy laws, including, but not limited to, the Health Insurance Portability and Accountability Act of 1996.

17.5 Investigator Responsibilities

By signing the Agreement of Investigator form, the Investigator agrees to:

1. Conduct the study in accordance with the protocol and only make changes after notifying the Sponsor (or designee), except when to protect the safety, rights or welfare of subjects.
2. Personally conduct or supervise the study (or investigation).
3. Ensure that the requirements relating to obtaining informed consent and IRB review and approval meet federal guidelines, as stated in § 21 CFR, parts 50 and 56.
4. Report to the Sponsor or designee any AEs that occur in the course of the study, in accordance with §21 CFR 312.64.
5. Ensure that all associates, colleagues and employees assisting in the conduct of the study are informed about their obligations in meeting the above commitments.
6. Maintain adequate and accurate records in accordance with §21 CFR 312.62 and to make those records available for inspection with the Sponsor (or designee).
7. Ensure that an IRB that complies with the requirements of §21 CFR part 56 will be responsible for initial and continuing review and approval of the clinical study.
8. Promptly report to the IRB and the Sponsor (or designee) all changes in the research activity and all unanticipated problems involving risks to subjects or others (to include amendments and IND safety reports).
9. Seek IRB approval before any changes are made in the research study, except when necessary to eliminate hazards to the patients/subjects.

10. Comply with all other requirements regarding the obligations of clinical investigators and all other pertinent requirements listed in § 21 CFR part 312.

[name], MSC
Clinical Research Protocol
INPATIENT CLINICAL TRIAL OF NAC IN ASTHMA (ICON)

Protocol Number:	17-24231
NCT Number	NCT03581084
Investigational Product:	n-acetylcysteine
Development Phase:	4
Sponsor:	[name], MSc [name]
Funding Organization:	NIH
Principal Investigator:	Name: [name], MSc [contact] [contact] E-mail: [contact]

STATISTICAL ANALYSIS PLAN

Our overarching method (experimental approach) is to test the efficacy of inhaled NAC delivered for 5 days to asthma patients who have baseline evidence of mucus plugs on CT lung scans. We will assess if the NAC treatment causes the mucus plugs to go away by the end of the treatment period and we will assess for reappearance of mucus plugs at 6 weeks and 3 months time. We will also examine whether any NAC associated decrease in mucus plugs is associated with improvement in FEV1. A primary analysis will be paired T-test analysis of the change in CT mucus plug score and in FEV1 from baseline to end treatment. Secondary analyses will look at the 6 week and 3 month time points.

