| DURATION OF SUBJECT PARTICIPATION AND DURATION OF STUDY | Subjects will be in the study for up to 91 days. Screening: up to 14 days Treatment: 5 days (subjects to be admitted to the hospital) Follow-up: 3 months The total duration of the study is expected to be 24 months. Subject recruitment will happen on a rolling basis. |
| CONCOMITANT MEDICATIONS | Prohibited: 
 • thiols and thiol derivatives • activated charcoal • inhaled insulin |
| EFFICACY EVALUATIONS | |
| PRIMARY ENDPOINT | The primary endpoint is the FEV1. Post-treatment FEV1 will be compared to pre-treatment baseline values. |
| SECONDARY ENDPOINTS | Secondary efficacy endpoints include: 
 • CT mucus score • FVC • PEF (AM and PM) • Air trapping (RV/TLC ratio) • FeNO • Blood eosinophils |
| OTHER EVALUATIONS | |
| SAFETY EVALUATIONS | Incidence of adverse events |
| PLANNED INTERIM ANALYSES | No interim analysis is planned. |
| STATISTICS Primary Analysis Plan | The primary analysis is a paired t-test analysis of the % change in FEV1 from the start to the end of the one week treatment period with four times daily NAC (Mucomyst-20). The secondary analysis will be to determine how the change in FEV1 relates to the change in CT mucus score. |
| Rationale for Number of Subjects | We propose a sample size of 30, which will provide us with the power to examine the effect of NAC in a subgroup of individuals with asthma who have CT evidence of intraluminal mucus and to identify the CT mucus score that performs best as a biomarker of treatment response to NAC. Participants will be enrolled if their CT mucus scores are ≥ 5.0 . To calculate sample size for the one-week treatment period study, we used FEV1 measures from 219 adults with asthma published in Corren et al. NEJM, 2011 ¹ . The authors found that the standard deviation for the change in FEV1 in liters from day 1 to day |

| | |
|--|---|
| | 
7 was 19%. Using a standard deviation of 19 and a two-sided alpha of 0.05, we calculate a sample size of 30 to have 80% power to detect a change in FEV1 of 10% (a reasonable effect size because early studies of Pulmozyme in CF reported a 10% increase in FEV1 at day 3 of treatment).⁷
 |
|--|---|

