5 CRITERIA FOR EVALUATION

5.1 Primary Efficacy Endpoint

FEV1 will be the primary endpoint because it is the most robust measure of airflow obstruction in asthma. We will compare post-treatment FEV1 to pre-treatment baseline values.

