5.2 Secondary Efficacy Endpoints

Secondary efficacy endpoints will include:

- CT mucus score
- FVC
- PEF (AM and PM)
- Air trapping (RV/TLC ratio)
- FeNO
- Blood eosinophils

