15 STATISTICAL METHODS AND CONSIDERATIONS

Prior to the analysis of the final study data, a detailed Statistical Analysis Plan (SAP) will be written describing all analyses that will be performed. The SAP will contain any modifications to the analysis plan described below.

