15.3 Analysis of Primary Endpoint

The primary analysis is a paired t-test analysis of the % change in FEV1 from the start to the end of the one week treatment period with four times daily NAC (Mucomyst-20). The secondary analysis will be to determine how the change in FEV1 relates to the change in CT mucus score.

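### The protocol makes FEV1 the sole primary endpoint, but the SAP's primary analysis tests CT mucus score and FEV1 together, with no success rule and power for FEV1 only

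*SAP*

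**What the plan says.** **Protocol, endpoints.** The Synopsis states "The primary endpoint is the FEV1", and Section 5.1 gives a reason: "FEV1 will be the primary endpoint because it is the most robust measure of airflow obstruction in asthma". Section 5.2 opens its list with "Secondary efficacy endpoints will include", and the first item is CT mucus score. The Synopsis has the same secondary list.

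**Protocol, analysis.** Section 15.3 begins "The primary analysis is a paired t-test analysis of the % change in FEV1 from the start to the end" of the treatment period. CT score enters Section 15.3 only through a relationship: "The secondary analysis will be to determine how the change in FEV1 relates to the change in CT mucus score". Section 15.4 adds that "we will explore if NAC treatment decreases levels of NO in exhaled breath or the numbers of eosinophils in peripheral blood". Section 15 therefore contains no test of the CT change itself.

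**Protocol, objective.** Section 3.1 has a single primary objective that joins two effects: fewer mucus plugs and better lung function.

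**Protocol, sample size.** Section 15.6 uses FEV1 inputs only: SD 19, change 10%, two-sided alpha 0.05, 80% power, N = 30. It also mentions finding the CT score that best predicts response. That is a different aim from testing the CT change, and no CT effect size or SD is given for it.

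**SAP.** Its one paragraph says: "A primary analysis will be paired T-test analysis of the change in CT mucus plug score and in FEV1 from baseline to end treatment". It contains no success rule, testing order, alpha statement or power statement.

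**Link between the two.** Protocol Section 15 says "The SAP will contain any modifications to the analysis plan described below".

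**The concern.** CT mucus score is secondary in one governing document and part of the primary analysis in the other. The SAP does not identify this as a change, and the protocol's endpoint sections still stand. A favourable FEV1 result could be called the primary success by citing the protocol. A favourable CT result could be presented as a primary finding by citing the SAP.

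The trial is single-arm and unblinded (Protocol Sections 4.1 and 8.2), so results are visible as they accrue. A fixed statement of which result decides the trial is one of its few safeguards against choosing the favourable result afterwards.

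The statistical consequence depends on the rule that is missing. An either-counts rule would raise the false-positive rate. A both-required rule would not, but the stated 80% power would then no longer describe the primary analysis.

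**Working it through.** **1. Reproduce the plan's sample size (FEV1 alone).** Inputs from Protocol Section 15.6: change 10, SD 19, two-sided alpha 0.05, power 80%, paired.

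- Normal formula: n = [SD × (z₀.₉₇₅ + z₀.₈₀) / change]² = [19 × (1.960 + 0.842) / 10]² = 28.3, rounded up to 29.
- Exact paired t at n = 30: standardised effect 10/19 = 0.526, noncentrality 0.526 × √30 = 2.88, 29 degrees of freedom; power = 79.6%. At n = 31 it is 80.9%.

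N = 30 is thus consistent with 80% power for FEV1.

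**2. If both tests are required.** Each is tested at 0.05 with no alpha penalty. Let c be the power of the CT test, which the documents do not allow one to compute. Whatever the correlation, joint power lies between max(0, c + 0.796 − 1) and min(c, 0.796).

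| Assumed CT power | Lowest joint power | Highest joint power |
|---|---|---|
| 80% | 59.6% | 79.6% |
| 90% | 69.6% | 79.6% |
| 99% | 78.6% | 79.6% |

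As one illustration, assume that CT score has the same standardised effect as FEV1 (0.526) and that the tests are independent. Joint power at n = 30 is then 0.796² = 63.3%. About n = 40 is needed for 80%: single-test power 90.1%, and 0.901² = 81.1%.

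**3. If either test may count at 0.05.** For independent tests, the chance of at least one false positive is 1 − 0.95² = 9.75%. For correlated tests (correlations assumed):

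| Correlation | Bivariate normal | Simulated paired t-tests, n = 30 |
|---|---|---|
| 0.3 | 9.5% | 9.6% |
| 0.5 | 9.1% | 9.1% |
| 0.7 | 8.3% | 8.4% |
| 0.9 | 7.0% | 7.1% |

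Splitting alpha to 0.025 each would remove the inflation, but it lowers FEV1 power at n = 30 to 69.7%; n = 37 would be needed for 80%.

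**4. If FEV1 is tested first and CT score only after a significant FEV1 result.** With no effect on either measure, a false claim requires a false positive on FEV1, so error is 5% (simulated 5.0% to 5.1%). With a true 10% FEV1 effect and no CT effect, the false CT claim rate is 0.796 × 0.05 = 4.0% for independent tests, falling to 2.7% at correlation 0.9. FEV1 keeps its full alpha, so its 79.6% power stands.

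**5. CT baseline.** The SAP says only baseline. No CT scan is taken on Day 1. Sections 9.1.14 and 10.2 and Appendix 1 place the screening scan at Visit 2 (Day -10). Section 10.3 also lists one at optional Visit 2b (Day -7). The next scan is at Visit 9 (Day 6). Any rule that gives CT score a confirmatory role must name the scan.

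**The case against.** The strongest reply is that the SAP never offers CT score alone as primary. Its sentence names both measures, and the primary objective in Section 3.1 is also conjunctive, so the best-supported reading of the pair is that both must succeed. Under that reading there is no error inflation, and the 9.75% figure needs a rule that no passage states. **This stands:** the case should rest on the conflicting designation, not on 9.75%. It does not settle the matter, because the SAP does not say that both must succeed, and the protocol names FEV1 alone.

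A second reply is that Section 15 defers detail to the SAP and lets it modify the analysis, so the CT test is supplied as intended. **This stands in part.** The permission covers the analysis plan in Section 15. The designations in the Synopsis and in Sections 5.1 and 5.2 lie outside it and are unchanged.

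Third, the power loss is not measured: it could be about one percentage point or about 20, depending on an assumed CT power. **This is correct.** The defect is that the plan gives no way to know.

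Fourth, testing FEV1 first demotes CT score against both the SAP and the objective. **This is fair.** The choice belongs to the sponsor; FEV1-first leads below only because it matches the stated sample size.

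Finally, this is a 30-subject phase 4 study in which FEV1 is tested either way. It nevertheless states a two-sided 0.05 test with 80% power, and that claim needs a defined target.

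**Conclusion.** The concern holds and should be corrected before analysis. The two documents give CT mucus score different status, and nothing in either says how the pair decides the trial.

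The stated 80% power is sound for FEV1 alone, given the plan's SD of 19 and change of 10%. With both required, error stays at 5% but joint power has a ceiling of 79.6% and no known floor. Only an either-counts rule would inflate error, to between about 7% and 9.75% over the correlations examined (0.9 down to 0). All CT power values and correlations here are assumptions, since the documents give none.

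**What to change.** Put one rule, in the same words, in both documents as early as possible and in any case before the final analysis. The SAP should label it as a modification of Protocol Section 15.

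**Rule that fits the stated sample size (FEV1 first):**

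> Primary analysis: percentage change in FEV1 between start and end of treatment, paired t-test, two-sided alpha 0.05. First secondary endpoint: change in CT mucus score between the screening scan (Visit 2, or the Visit 2b scan where one was taken) and Visit 9, tested at two-sided 0.05 only if the FEV1 test is significant, and otherwise reported with a 95% confidence interval. The 80% power applies to FEV1 only.

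Using this text in both places also settles the scale: the protocol analyses percentage change in FEV1, while the SAP says only change. It does not settle whether the primary FEV1 is pre- or post-bronchodilator, which is a separate question.

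**Alternative (co-primary):** if the sponsor wants the SAP's pair to stand, which matches Section 3.1, declare both tests required at two-sided 0.05. Amend the Synopsis and Sections 5.1 and 5.2, use the same CT baseline, and state that power for the pair is not established.

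**Cost.** Either option is a wording change at N = 30.

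- Under FEV1-first, a CT result is not confirmatory if FEV1 fails, and the joint objective is fully met only if both tests succeed. The 5% error control covers these two tests, not the remaining secondary endpoints.
- Under co-primary, joint power is at most 79.6% and otherwise unknown. Establishing 80% for the pair would need CT assumptions and possibly more subjects: about 40 in the equal-effect, independent illustration above.
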